### After Week 4:

Subjects classified as clear at any of the on-treatment visits may stop the treatment at the investigator's discretion. They should remain in the trial and attend all visits up to and including the follow-up visit. The IPs will continue to be dispensed to the subject, and treatment may be restarted at the subject's discretion. The subject should not discontinue treatment themselves between visits, but is only allowed to stop using the treatment on the advice of the investigator at a scheduled visit.

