### 10.4 Study Drug Exposure and Accountability

Subjects will record the date of each trial medication application in the subject diary. The kit number, and corresponding date dispensed and returned will be collected.

The weight of the returned kits will also be collected.

The following parameters of study medication exposure will be summarized by treatment group and by study period, i.e., from day 1 to Week 4 (both groups) and from day 1 to Week 8 (MC2-01 cream group), for the Safety Population:

- Total number of days of exposure to the study drug, defined as the date of last application of study drug during the period minus date of first application plus one. The last application is the in-clinic dosing at Week 4 visit (Day 1 to Week 4 period) and Week 8 visit (Day 1 to Week 8 period).
- Total number of missed doses during each study period per subject diary
- Total number of applications during each study period, defined as the total number of doses required minus total number of doses missed. Total number of required doses is defined as total number of days of exposure minus any days of investigator approved stop (if applicable)
- Total weight of trial medication used (g) during each study period, defined as the summation of amount of drug used for all dispensed kits. Amount of drug used per kit is defined as the difference in weight between the returned and dispensed kits, where weight

of dispensed kits is a unit value. Amount of drug used for sealed and unreturned kits will be assumed to be 0.0 g

- Amount of drug used per week (g/per week), defined as the total amount of drug used divided by total number of days of exposure to the study drug multiplied by 7

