[2] Total number of doses applied= total number of doses required – total number of missed doses. Total number of doses required = total number of days of exposure – any days of investigator approved stop.

Table 14.1.3: Summary of Extent of Exposure and Compliance  
Safety Population

	Day 1 to Week 8	Day 1 to Week 4	
	MC2-01 Cream (N=XX)	MC2-01 Cream (N=XX)	Active Comparator (N=XX)
Total Amount of Drug Used (g)[3]			
N	XX	XX	XX
Mean (SD)	XX.X (XX.X)	XX.X (XX.X)	XX.X (XX.X)
Median	XX.X	XX.X	XX.X
Q1, Q3	XX, XX	XX, XX	XX, XX
Minimum, Maximum	XX, XX	XX, XX	XX, XX
Amount of Drug Used per Week (g/per week)[4]			
N	XX	XX	XX
Mean (SD)	XX.X (XX.X)	XX.X (XX.X)	XX.X (XX.X)
Median	XX.X	XX.X	XX.X
Q1, Q3	XX, XX	XX, XX	XX, XX
Minimum, Maximum	XX, XX	XX, XX	XX, XX

[3] Total amount of drug used (g) is defined as the summation of amount of drug used per kit for all returned kits. Amount of drug used per kit is the difference in weight between the returned and dispensed kits. Amount of drug used for sealed and unreturned kits will be assumed to be 0.0 g.

[4] Amount of drug used per week (g/per week) is defined as the total amount of drug used divided by total number of days of exposure to the study drug multiplied by 7.

Generated on XX/XX/XX:XXXX by SMYDM / Uses: XXXX / Reference: Data Listing XXXX

Table 14.1.4: Summary of Concomitant Medications  
by Anatomical Therapeutic Chemical Class (ATC) and Preferred Term  
Safety Population

	MC2-01 Cream (N=XX)	Active Comparator (N=XX)
Subjects with any Concomitant Medication, n (%)	XX (XX.X)	XX (XX.X)
<< Anatomical Therapeutic Chemical Class >>		
<< Medication Preferred Term >>	XXXXX	XXXXX
<< Medication Preferred Term >>	XXXXX	XXXXX
<< Medication Preferred Term >>	XXXXX	XXXXX
<< Anatomical Therapeutic Chemical Class >>		
<< Medication Preferred Term >>	XXXXX	XXXXX
<< Medication Preferred Term >>	XXXXX	XXXXX
<< Medication Preferred Term >>	XXXXX	XXXXX

Note: Any medication ongoing or with stop date on or after Day 1 is a concomitant medication. Counts reflect number of subjects in each treatment group reporting one or more prior medication that map to the WHO Drug anatomical therapeutic chemical or preferred term. A subject may be counted once only in each row of the table.

Generated on XX/XX/XX:XXXX by XXXXX / Uses: XXXX / Reference: Data Listings XXXX

MC2 Therapeutics  
Protocol Number: MC2-01-C3

Page X of Y

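### Grams per week for Day 1 to Week 8 is divided by a span that keeps approved stop days and presumes a Week 8 dose, so for cream subjects who stop it can fall well below use while on treatment

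*SAP*

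**What the plan says.** SAP 10.4 builds the exposure measures in sequence.

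- Days of exposure is "defined as the date of last application of study drug during the period minus date of first application plus one". The next sentence identifies that last application as the in-clinic dose at the Week 4 visit for the first period "and Week 8 visit (Day 1 to Week 8 period").
- Approved stops enter at the next step only: "Total number of required doses is defined as total number of days of exposure minus any days of investigator approved stop (if applicable"). Applications are then required doses minus missed doses.
- Weekly use goes back to the unadjusted span: "defined as the total amount of drug used divided by total number of days of exposure to the study drug multiplied by 7". Footnote 4 of Table 14.1.3 repeats it ("Amount of drug used per week (g/per week) is defined as the total amount of drug used divided by total number of days"), as do the notes to Listings 16.2.5.3.1 and 16.2.5.3.2.

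The Protocol foresees time off cream inside that span. Under the After Week 4 heading of section 6.4, "Subjects classified as clear at any of the on-treatment visits may stop the treatment at the investigator's discretion". Such subjects stay in the trial, still receive product, and "treatment may be restarted at the subject's discretion". A subject is "only allowed to stop using the treatment on the advice of the investigator at a scheduled visit".

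There is a second route. Under Protocol 7.9.2, a cream subject with HPA-axis suppression at Week 4 is told to discontinue the cream but remains in the trial for a repeat ACTH test at Week 8. SAP 10.8.2.1 reports the Week 8 result by Week 4 suppression status.

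**The concern.** The SAP treats approved stop days as non-dosing time in one exposure measure and leaves them in the denominator of another in the same section. Naming the Week 8 dose as the last application also does not fit a subject who has no such dose.

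Both objectives are set under maximum-use conditions, and g/week is the only tabulated exposure measure on the scale of the 100 g weekly limit in Protocol 6.3. Table 14.1.3 prints the cream arm's Week 8 and Week 4 columns side by side. A fall between them could mean that subjects used less when they applied, or that some did not apply at all for part of the period. The planned figure cannot separate the two. For subjects who stopped because of suppression, a wrong exposure period would sit beside the HPA result it should help interpret.

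**Working it through.** The documents state no g/week value, so there is no plan figure to reproduce. This is direct arithmetic on the definitions.

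**Inputs**
- Protocol Table 7-2: first application at Day 0; Week 4 at Day 28, Week 6 at Day 42 and Week 8 at Day 56, each ± 2 days.
- Illustrative use while applying: 100 g/week, the limit in Protocol 6.3. The percentages do not depend on this choice.
- Total grams are taken as correctly measured.

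**Formulas**, with D = exposure days, S = stop days and G = grams used:
- SAP figure = 7 × G / D
- On-treatment figure = 7 × G / (D − S)
- Relative shortfall = 1 − (D − S)/D = S/D

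With a Week 8 dose at nominal days, D = 56 − 0 + 1 = 57.

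**Cases at nominal visit days**

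| Case | S | Days applied | Grams | SAP g/week | Shortfall |
|---|---|---|---|---|---|
| Stop after the Week 4 clinic dose (Days 29–55), dosed at Week 8 | 27 | 30 | 428.6 | 52.6 | 27/57 = 47.4% |
| Stop at Week 6, that day's dose applied (Days 43–55), dosed at Week 8 | 13 | 44 | 628.6 | 77.2 | 13/57 = 22.8% |
| Stop at Week 6, that day's dose not applied (Days 42–55), dosed at Week 8 | 14 | 43 | 614.3 | 75.4 | 14/57 = 24.6% |
| Cream ended at Week 4, no Week 8 dose, last application taken literally as Week 8 | 28 | 29 | 414.3 | 50.9 | 28/57 = 49.1% |

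Example, first row: 100/7 × 30 = 428.6 g; 7 × 428.6/57 = 52.6 g/week.

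**Visit windows.** The first row ranges from 23/55 = 41.8% (Week 4 late, Week 8 early) to 31/59 = 52.5% (the reverse). The second row ranges from 9/55 = 16.4% to 17/59 = 28.8%.

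**Last row under the other reading.** If the actual last application (Day 28) is used, D = 29 and 7 × 414.3/29 = 100 g/week, so there is no shortfall. The result turns entirely on which of the two adjacent SAP sentences the programmer follows. A suppressed subject is contacted after the Week 4 test, so cream may end slightly after Day 28; 29 application days is approximate.

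**Arm mean.** If a share p of cream subjects takes the longest pause, and all use the same amount while applying, the mean falls by p × 47.4%. For assumed values p = 20% and 40% this is 9.5% and 19.0%. The documents support no particular p.

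**The case against.** The strongest reply is that the figure is correct for what its footnotes say it is: grams over the first-to-last-application span. A subject who paused really did average less over eight weeks. This stands. The shortfall is relative to use while on treatment, not to an error in the calendar average.

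A reader might infer that the calendar average should be replaced. The documents do not support that. In a paused subject, the Week 8 ACTH test and 24-hour urine collection come before that day's application, so they follow cream-free days. An on-treatment rate printed alone would imply recent use that did not occur.

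A reader might also infer that the Week 8 column as a whole will be about half the true value. That does not follow either. The 47% case needs a subject with 20% to 30% BSA involvement to be clear at Week 4, an investigator who chooses to stop, no restart for four weeks, and then a Week 8 dose. The After Week 4 heading does not settle whether the Week 4 visit counts, and nothing says that a paused subject is dosed at Week 8.

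The 49% case can be answered by reading the sentence about in-clinic dosing as describing the scheduled course only. That is possible, but the wording is unconditional and is repeated in footnote 1 of Table 14.1.3.

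Finally, consequences are limited. The between-arm exposure comparison is at Week 4, where subjects clear at Week 2 are generally told to continue. G/week enters no model, endpoint or population definition. Total grams and applied doses are also tabulated, so a reader could recompute an alternative.

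**Conclusion.** The inconsistency is real and worth correcting, as a matter of exposure reporting rather than of the primary analysis. For cream subjects who pause after Week 4 and are dosed at Week 8, printed g/week is below on-treatment use by stop days over exposure days: at most 47% at nominal days if a stop at the Week 4 visit is allowed, and about 23% to 25% if the first stop is at Week 6. For subjects whose cream ended at Week 4 without a Week 8 dose, including those stopped for HPA-axis suppression, the literal rule gives 57 exposure days for about 29 application days, a 49% understatement. In that case the exposure-days row is wrong as well.

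These are subject-level figures. The effect on the arm mean cannot be stated without stop rates, which the documents do not give. The Week 4 comparison is largely unaffected.

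**What to change.** Amend SAP 10.4, footnotes 1 and 4 of Table 14.1.3, and the notes to Listings 16.2.5.3.1 and 16.2.5.3.2 as follows.

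1. Take the last application in each period from the actual date in the diary or clinic record, not by default from the Week 4 or Week 8 visit. Count stop days and missed doses only up to that date.
2. Keep the existing g/week, labelled as a calendar average over the first-to-last-application span. Add an on-treatment row: 7 × grams / (exposure days − stop days up to the last application).
3. Derive restarts from the daily diary (Listing 16.2.5.4.1), because Listing 16.2.5.1 shows an approved stop date but no restart date.

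For a subject who never restarts, the two rates will coincide after step 1; the shorter exposure then shows in the exposure-days row, which should be read with them.

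The cost is SAP wording, one extra table row with matching listing columns, and a small derivation from data already collected. Nothing in trial conduct changes.

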## 10.5 Prior and Concomitant Medications

Prior (with stop dates prior to Day 1) and concomitant medications (ongoing or with stop dates on or after Day 1) for all randomised subjects will be provided in a by-subject listing. Concomitant medications will be summarized by WHO-DDE Anatomical-Therapeutic-Chemical (ATC) classification and preferred term (PT) for each treatment for Safety population.

For the determination of prior vs. concomitant medications, the following rules regarding the stop date will be applied:

- If only year was recorded, and it is before Day 1, it is a prior medication; if year is same or after Day 1, it is assumed to be a concomitant medication.
- If day is missing, but month and year are before Day 1, it is a prior medication; if month and year are the same or after Day 1, it is assumed to be a concomitant medication.
- If start date is after Day 1, it is a concomitant medication regardless.

Psoriasis treatment history will be displayed in a by-subject listing.

## 10.6 Concurrent Procedures

All concurrent procedures will be provided in a by subject listing for all randomized subjects.

## 10.7 Medical History

Past and current medical conditions will be coded using MedDRA dictionary (version 20.0). Medical history for all randomized subjects will be provided in a by-subject listing.

## 10.8 Safety Analysis

### 10.8.1 Safety Endpoints

Primary safety endpoints include:

- HPA-axis suppression

HPA-axis function will be assessed in a challenge test with an intravenous dose of adrenocorticotropic hormone (ACTH) (Cosyntropin). **Normal HPA function** is, based on the Cosyntropin US Packing Insert (USPI) (revision May 2018), defined as a 30-minute post-stimulation cortisol level  $\geq 18 \mu\text{g/dL}$ .

Conversely, **HPA-axis suppression** is defined as 30-minute post-stimulation cortisol level <18 µg/dL.

HPA-axis function status will be considered as missing if post-stimulation serum cortisol level is missing.

- Changes in calcium metabolism endpoints from 24-hour urinalysis, including
  - Albumin-corrected serum calcium
  - 24 hours urinary calcium excretion
  - Ratio of urinary calcium to creatinine

Other safety endpoints include:

- Adverse events (AEs)
- Local Skin Reaction (LSR) Assessment
  - Investigator assessed signs: erythema, scaling, edema, atrophy, vesicles and erosion/ulceration; vesicles, and erosion/ulceration
  - Subject assessed symptoms: burning or pain
- Laboratory parameters
  - Hematology: hemoglobin, hematocrit, red blood cell (RBC) count, mean corpuscular volume (MCV), white blood cell (WBC) count, including differential count and platelet count.
  - Serum biochemistry: cortisol, urea, glucose, creatinine, calcium, albumin, calcium (albumin corrected), sodium, potassium, chloride, calcium, phosphate, alkaline phosphatase (ALP), plasma parathyroid hormone (PTH), 25-OH Vitamin D (Visit 1 only)
  - 24-hour urinalysis: calcium, phosphate, creatinine, volume, total calcium excretion, total phosphate excretion, total creatinine excretion, urinary calcium:creatinine ratio, urinary phosphate:creatinine ratio
- Vital signs (blood pressure, pulse rate)
- Standard 12-lead electrocardiogram (ECG) (MC2-01 cream subjects only)
- Physical examination (PE)

## 10.8.2 Analyses of Safety Endpoints

### 10.8.2.1 HPA-axis Suppression

The number and proportion of subjects with HPA-axis suppression at Week 4 will be summarised for the HPA population. Subjects with HPA-axis suppression at Week 4, was as described in the

protocol, contacted to discontinue use of MC2-01 cream. Subjects with HPA-axis suppression at Week 8 will be summarised overall and separately by HPA-axis suppression status at Week 4.

An additional analysis of the number and proportion of subjects with HPA-axis suppression will be summarised based on the test laboratory normal reference range established for the analytical method used by the test laboratory in the trial for the ACTH challenge test.

- In this analysis HPA suppression is defined as a 30-minute post-stimulation cortisol level  $< 14 \mu\text{g/dl}$  (test laboratory normal reference range of 14 to 36  $\mu\text{g/dl}$  for the 30-minute post-stimulation cortisol level). This analysis will be performed among MC2-01 cream subjects whose Baseline cortisol level is  $\geq 14 \mu\text{g/dl}$

All HPA-axis function test results (baseline, Week 4, Week 8, and Follow-up) will be presented in a by-subject listing for the Safety population.

#### **10.8.2.2 Calcium Metabolism Endpoints**

All calcium metabolism data will be presented in a by-subject listing for the following parameters:

- Albumin-corrected serum calcium
- 24 hours urinary calcium excretion
- Ratio of urinary calcium to creatinine

Observed values and changes from baseline to Week 4 and Week 8 will be summarized using descriptive statistics for subjects in the Safety population assigned to MC2-01 cream.

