Overdosage with topical CAL can cause hypercalcemia due to the systemic absorption of CAL, which then affects calcium metabolism as it is a vitamin D analogue. However, extensive experience with topical use of CAL in psoriasis has demonstrated no significant impact on calcium metabolism, when used in the recommended amounts (maximum weekly dose in adults of 100 g of a 50 mcg/g concentration). Doses up to 300 g have been used with serum calcium remaining within the reference range. Calcium metabolism will be evaluated in the present study by measurement of albumin corrected serum calcium, phosphate, alkaline phosphatase and plasma PTH before, during and after treatment. A 24-hour urine sample will be collected and the urinary calcium phosphate, sodium and creatinine will be measured and the urinary calcium:creatinine and phosphate:creatinine ratios will be calculated. It is well-established that there is a relationship between dietary calcium intake and the urinary calcium excretion in adults. The urinary excretion of calcium has been reported to increase by 6-19 mg with each additional 100 mg of calcium intake22:23. Subjects will not be asked to change their diet during the study, but in order to limit diet-related variability in urinary calcium excretion, their normal consumption of calcium-rich foods will be reviewed and should be kept constant during 3 days prior to and during each 24-hour urinary collection. Considering that dairy products account for the majority of the of calcium absorption in most people, this protocol focusses on the intake of dairy products. The subjects will keep a diary of the daily intake of dairy products, calcium-fortified products (e.g. bread, cereals, orange juice or soy milk) and other specified calcium-rich products. The number of daily servings of calcium defined as 240 mL (one US cup) in dairy products such as milk or yoghurt or of a calcium-fortified product with corresponding calcium content (300 mg calcium per 240mL/one US cup) or 42g (1.5 ounces) of cheese. As an extreme calcium intake has been shown to significantly increase urinary excretion of calcium, subjects will be instructed not to consume more than five daily calcium servings (i.e. 1500 mg calcium). The combination of high calcium intake with vitamin D supplementation significantly increases urinary calcium. Hence the use of calcium or vitamin D supplements were excluded in this study with the exception of stable doses of oral vitamin D (up to 400 IU/day) at baseline with no dose adjustment during the study period. Systemic safety of MC2-01 cream on calcium metabolism and HPA axis will be assessed at Week 4 and Week 8. Experience with the current commercially available fixed-dose combinations of CAL and BDP has shown that effects on HPA axis suppression or calcium homeostasis are infrequent events. For this reason, post-Baseline HPA

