
axis suppression and calcium homeostasis testing will be performed only in subjects receiving the MC2-01 cream, without any comparison to the reference compound.

Data from this trial, together with the measurements of albumin-corrected serum calcium and the calcium:creatinine ratio in urine samples in the phase 3 trial with MC2-01 cream are expected to provide adequate information with respect to the systemic safety of the MC2-01 cream.

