##### Calcium metabolism evaluation for subjects assigned to the MC2-01 cream:

Changes from Baseline to Week 4 or Week 8 in:

- Albumin-corrected serum calcium;
- 24-hour urinary calcium excretion;
- Ratio of urinary calcium to creatinine.

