## 7.2 Visit Schedule and Assessment for Subjects Assigned the MC2-01 Cream

**Table 7-2 Visit Schedule for Subjects Assigned to the MC2-01 Cream**

	Visit 1	Visit 2	Visit 3	Visit 4	Visit 5	Follow- up Visit a
	Day 0	Week 2	Week 4	Week 6	Week 8	
Examination	Day 0	Day 14 ± 2	Day 28 ± 2	Day 42 ± 2	Day 56 ± 2	
Inclusion/exclusion criteria	X					
Urine pregnancy test (UPT) b	X		X		X	
Demographics, medical history	X					
Prior and concomitant medication	X	X	X	X	X	
Physical examination	X c		X		X	
PGA	X	X	X	X	X	
Body Surface Area (BSA) involvement	X		X		X	
Vital signs	X	X	X	X	X	
Laboratory assessments	X		X	(X) d	X	X
Review food diary	X		X		X	
24-h urine collection	X	Instruct	X	Instruct	X	
Randomisation	X					
PK pre-dose blood sample (Single)	X	X				
PK serial blood samples e		Instruct	X	Instruct	X	
12-Lead ECG	X		X		X	
ACTH challenge test f	X		X		X	X
Psoriasis Treatment Convenience Scale			X			
Dispense IP and diary for compliance	X	X	X	X		
Collect IP		X	X	X	X	
Compliance		X	X	X	X	
Adverse event(s) g	X	X	X	X	X	X
Local Skin Reactions	X	X	X	X	X	

- a) A follow-up visit is required to check: abnormal albumin-corrected serum calcium, HPA axis suppression, or unsolved treatment-related AEs at Week 8.
- b) For female subjects of childbearing potential.
- c) Including height and weight
- d) If serum albumin-corrected serum calcium is above the reference range at Week 4, a repeat test should be performed at Week 6.
- e) Blood samples for PK analysis are drawn before IP application (pre-dose sample) and 0.5, 1, 2, 3, 5 and 7 hours after IP application.
- f) The ACTH challenge test must be performed at 8 am ( $\pm 30$  minutes) before application of the IP.
- g) AEs are to be collected from the date of signing informed consent, i.e., during the washout period.

**Instruct:** At the indicated visits, instruct the subjects as to appropriate trial procedures as specified below:

- **Food diary:** instruct the subjects on how to use the food diary, especially recording their intake of calcium-rich nutrients
- **24-hour urine collection:** instruct the subjects on how to perform the 24-hour urine collection. Consumption of calcium-rich foods should be kept constant during and 3 days prior to each 24 hour urine collection.

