### **7.9.3 Food diary: calcium-rich nutrients**

All subjects should record their consumption of calcium-rich nutrients (mainly milk, other dairy products, calcium-fortified products) three days before and during the 24-hour urine collection prior to Visit 1/Day 0.

For subjects assigned to the MC2-01 cream, the same procedure will be followed before the Week 4 and Week 8 visits.

Based on the diary entries, the number of daily calcium servings should be calculated for each day and recorded in the eCRF.

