**Listing Tables**

16.1.7	Subject Enrolment and Randomization
16.2.1.1	Screen Failure

16.2.1.2	Subject Disposition
16.2.2	Protocol Deviations
16.2.3	Population Datasets
16.2.4.1	Demographics and Baseline Characteristics
16.2.4.2	Prior and Concomitant Medication
16.2.4.3	Concurrent Procedures
16.2.4.4	Medical or Surgical History
16.2.4.5	Psoriasis Treatment History
16.2.5.1	Study Drug Administration and Compliance
16.2.5.2	Study Drug Accountability
16.2.5.3.1	Overall Study Drug Exposure and Compliance, Day 1 to Week 4 Period
16.2.5.3.2	Overall Study Drug Exposure and Compliance, Day 1 to Week 8 Period
16.2.5.4.1	Subject Treatment Diary Card
16.2.5.4.2	Subject Food Diary
16.2.6.1	Plasma Concentration Sample Date and Time and Plasma Concentrations
16.2.6.2.1	CAL Derived Pharmacokinetics Parameters
16.2.6.2.2	BDP Derived Pharmacokinetics Parameters
16.2.6.2.3	MC1080 Derived Pharmacokinetics Parameters
16.2.6.2.4	Betamethasone 17-propionate Derived Pharmacokinetics Parameters
16.2.6.3	Physician's Global Assessment of Disease Severity (PGA) – Scalp, Trunk and/or Limbs
16.2.6.4	Investigator's Assessment of the Body Surface Area (BSA) Involvement of Psoriasis
16.2.6.5	Investigator and Subject Assessed Local Skin Reaction (LSR)
16.2.6.6	Psoriasis Treatment Convenience Scale
16.2.6.7	ACTH Challenge (<18 µg/dL.)
16.2.6.7	ACTH Challenge (<14 µg/dL.)
16.2.7.1	Adverse Events
16.2.7.2	Serious Adverse Events
16.2.7.3	Adverse Events Leading to Study Drug Discontinuation
16.2.8.1	Urine Pregnancy Test
16.2.8.2.1	Clinical Laboratory Test Results; Biochemistry
16.2.8.2.2	Clinical Laboratory Test Results; Hematology
16.2.8.2.3	Clinical Laboratory Test Results; 24 Hour Urinalysis
16.2.8.3	Laboratory Values Outside of Normal Range
16.2.8.4	Vital Signs
16.2.8.5	Physical Examinations
16.2.8.6	12-Lead ECG Results
16.2.9	General Comments

Table 14.1.1: Summary of Subject Disposition

	MC2-01 Cream	Active Comparator	Overall
Number of Subjects Screened			XX
Number of Subjects Randomized	XX	XX	XX
Number of Subjects in Safety Population, n (%)	XX (XX.X)	XX (XX.X)	XX (XX.X)
Number of Subjects in HPA Population, n (%)	XX (XX.X)	XX (XX.X)	XX (XX.X)
Number of Subjects in PK Population, n (%)	XX (XX.X)	XX (XX.X)	XX (XX.X)
Number of Subjects Completing the Study, n (%)	XX (XX.X)	XX (XX.X)	XX (XX.X)
Number of Subjects Discontinued, n (%)	XX (XX.X)	XX (XX.X)	XX (XX.X)
Reason for Discontinuation, n (%)			
Investigator discretion	XX (XX.X)	XX (XX.X)	XX (XX.X)

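### The two urinary calcium endpoints are uncontrolled before-after changes, and the recorded calcium servings that would show whether diet stayed similar are only listed

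*SAP*

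**What the plan says.** Protocol 4.2 lists three calcium endpoints for the cream arm, each a change from baseline to Week 4 or Week 8: "Albumin-corrected serum calcium", "24-hour urinary calcium excretion" and the urinary calcium to creatinine ratio. Calcium metabolism is part of the secondary objective, and Protocol 8.8 counts it among the primary safety endpoints.

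Protocol 2.2 says of testing after baseline: "axis suppression and calcium homeostasis testing will be performed only in subjects receiving the MC2-01 cream, without any comparison to the reference compound". Protocol 7.9.4 agrees: all subjects collect urine before Day 0, but only cream subjects do so before Weeks 4 and 8.

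On diet, Protocol 2.2 states: "The urinary excretion of calcium has been reported to increase by 6-19 mg with each additional 100 mg of calcium intake". It sets a serving at 300 mg of calcium and caps intake at five servings (1500 mg) a day. Subjects are not asked to alter their diet. Table 7-2 adds: "Consumption of calcium-rich foods should be kept constant during and 3 days prior to each 24 hour urine collection". Under Protocol 7.9.3 a diary covers the three days before and the day of each collection, and "the number of daily calcium servings should be calculated for each day and recorded in the eCRF".

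SAP 10.8.2.2 plans: "Observed values and changes from baseline to Week 4 and Week 8 will be summarized using descriptive statistics for subjects in the Safety population", limited to the cream arm. The servings appear in the SAP only as by-subject Listing 16.2.5.4.2, "Subject Food Diary". No table, covariate or sensitivity analysis uses them.

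**The concern.** A before-after change attributes to treatment whatever else moved between visits. For urinary calcium the protocol itself identifies one such factor, gives its size, and collects the data needed to check it. The analysis plan then leaves those data in a listing that shows servings day by day, with no visit mean and no change.

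The creatinine ratio does not settle the matter. It guards against incomplete collection, but intake changes the calcium in the numerator.

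At stake is how the urinary results can be read. If average intake fell between baseline and Week 8, a rise in calcium excretion due to the drug could be hidden; if it rose, a diet effect could look like a drug effect. Protocol 2.2 names serum calcium and the calcium:creatinine ratio as what the phase 3 trial will contribute, so on these documents the 24-hour excretion result comes from this trial alone.

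**Working it through.** **Inputs from the documents**
- Calcium per serving: 300 mg (Protocol 2.2).
- Effect of intake on urinary calcium: 6 to 19 mg per 100 mg (Protocol 2.2).
- Cap: five servings a day (Protocol 2.2).
- Subjects: about 25 per arm in the PK population at Week 4 (Protocol 8.2). About 60 enrolled 1:1 (Protocol synopsis) gives 60 / 2 = 30 per arm.

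**The plan's own figure.** 5 servings × 300 mg = 1500 mg, which matches the protocol. The sample size is expressly not derived statistically, so there is nothing to reproduce there.

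**Size of a diet shift.** Change in urinary calcium = change in servings × 300 mg × (6 to 19) / 100.

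| Mean change in servings/day | Change in 24-hour urinary calcium (mg/day) |
|---|---|
| 0.5 | 9 to 28.5 |
| 1 | 18 to 57 |
| 2 | 36 to 114 |
| 5 (zero to the cap) | 90 to 285 |

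**Comparison with sampling error.** The documents give no SD for the change in urinary calcium. I assume 50 to 125 mg/day. The 95% half-width of a one-arm mean change is t(0.975, n−1) × SD / √n.
- n = 25: SE 50/5 = 10 to 125/5 = 25; half-width 20.6 to 51.6 mg/day.
- n = 30: half-width 18.7 to 46.7 mg/day.

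Mean shift in servings that equals the half-width at n = 25:
- at 57 mg per serving: 20.6/57 = 0.36 to 51.6/57 = 0.91 servings/day;
- at 18 mg per serving: 20.6/18 = 1.15 (unrounded half-width) to 51.6/18 = 2.87 servings/day.

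At the upper coefficient, a one-serving mean shift (57 mg/day) exceeds the half-width for every assumed SD. At the lower coefficient (18 mg/day) it stays inside for every assumed SD, at n = 25 and at n = 30.

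**Mean shift against individual variation.** Only a shift common to the group biases the mean change. Subject-to-subject variation in diet adds noise, and that noise is already contained in the SD of change that Table 14.2.5 will report.

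**What adjustment would do.** Regress change in urinary calcium on change in mean servings: change = a + b × (change in servings). The intercept is a = (mean change) − b × (mean change in servings), the expected change for a subject whose servings did not change. Random error in the serving count pulls b toward zero, so only part of any diet shift would be removed.

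**Population.** SAP 10.8.2.2 specifies the Safety population, and SAP 8 assigns that population to every safety analysis except the HPA axis. Table 14.2.5 is titled HPA Population, both in the SAP 14 outline and in its shell. That population leaves out cream subjects without normal HPA function at baseline, so the two need not contain the same subjects.

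**The case against.** The strongest reply is that the protocol already controls diet. It has habitual intake reviewed and kept constant around each collection, caps extreme intake, restricts calcium and vitamin D supplements (Protocol 5.3), and has the food diary reviewed at Day 0, Week 4 and Week 8. The natural reading is that subjects keep to their usual intake at every collection. This stands, and it should reduce any shift. What it does not do is verify the result: no planned summary compares servings between visits.

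It is also fair that nothing in the documents points to a shift common to the group, so the figures above are hypothetical. The 6 to 19 mg range comes from two cited studies whose titles concern young females and young girls; applying it to within-subject change in adults of both sexes is an extrapolation, though one the protocol itself makes.

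The lack of a control is a disclosed design choice, the analysis is descriptive with no test, and by-subject servings and urinary changes are both listed, so an outlying subject could be checked by hand. Listings do not show the average shift, however, and that is what matters for the mean.

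A regression on a coarse, dairy-focused count in about 25 subjects could look more diet-corrected than it is. That is a reason to label it as partial and to keep the unadjusted change beside it.

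**Conclusion.** The two urinary endpoints are uncontrolled before-after changes, and the servings recorded in the eCRF enter no planned summary. By the protocol's own coefficient, one serving a day in mean intake corresponds to 18 to 57 mg/day of urinary calcium. Set against an assumed SD of change of 50 to 125 mg/day and n = 25, that runs from inside the 95% half-width to beyond it. Whether any such shift occurs is unknown.

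Two stronger readings are not supported. A reader might infer that the calcium objective as a whole rests on uncontrolled urinary data. It does not: albumin-corrected serum calcium is the first-listed endpoint, it triggers the repeat test and the follow-up visit (Protocol 7.9.1 and 7.15), and it is measured in both arms at Day 0 and Week 4. SAP 10.8.2.5 summarises it by treatment and visit, so a descriptive concurrent comparison exists at Week 4. A reader might also infer that the urinary results are biased by diet. The documents show only that the plan would not reveal a shift if there were one.

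The consequence is limited interpretability of a descriptive summary. It merits a change because the data are already collected and the edit is small.

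**What to change.** In SAP 10.8.2.2 and Table 14.2.5:

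1. Summarise mean daily calcium servings (three diary days plus the collection day) at baseline, Week 4 and Week 8, and the change from baseline.
2. Beside the unadjusted change, report for 24-hour urinary calcium and for the calcium:creatinine ratio a sensitivity estimate from linear regression of change on change in mean servings: the mean at zero change in servings, with a 95% CI, at Week 4 and Week 8. Label it a partial adjustment, because servings measure intake coarsely and the sample is about 25 to 30. State that it does not replace a control arm.
3. Reconcile the HPA Population title of Table 14.2.5, in the SAP 14 outline and the shell, with the Safety population in SAP 10.8.2.2, so that the added panel has one defined denominator.

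The cost is SAP wording and one table panel, with no new procedure or data. The downsides are one extra parameter in a small sample and the loss of subjects without diary data from the adjusted estimate; the unadjusted summary keeps them.
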